6. SPECIFIC AIMS

AIM 1. To compare the proportion of persons with HIV and out of care (PWH-OOC) undergoing rapid-ART initiation that are on ART with VL \leq 50 copies/mL at week 24 between those randomized to 60-Minutes-for Health vs. a time-and-attention control session at baseline.

AIM 2. To compare the proportion of participants in care at week 24 between those randomized to 60-Minutes-for Health vs. a time-and-attention control session at baseline.

AIM 3. To compare the role of genotypic susceptibility scores (GSS) derived from HIV Genosure archive resistance testing as a predictor of achieving virologic suppression on rapid ART among PWH-OOC.

AIM 4. To determine the acceptability of rapid ART among PWH-OOC using quantitative surveys and focus groups on patient-reported outcomes and perspectives at week 4.

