9. RESEARCH DESIGN AND METHODS

The overall strategy is to perform a feasibility study of rapid ART initiation among PWH-OOC who are randomized (1:1) to an unblinded behavioral intervention “60-Minutes-for Health”, compared to a 60 minute time-and-attention control session focused on diet and nutrition.

Individuals eligible for participation will be enrolled and followed for 48 weeks. They will be offered a same day (or within 1 week) appointment to enable the initiation of ART within 7 days of contact. Eligible individuals, after completing informed consent, will start ART for HIV with Bictegravir/Emtricitabine/tenofovir alafenamide (B/F/TAF) or appropriate alternative therapy if B/F/TAF is not thought to be an optimal regimen. Individuals will undergo computer-generated randomization (1:1) to onsite 60-Minutes-for Health intervention vs an onsite theory-based time-and-attention control session focused on diet and nutrition. After completion of the intervention participants will receive standard-of-care case management services between day 0 and week 4. A 60-day supply of B/F/TAF or alternative will be provided for participants of both study arms. The timeline of visits and study interventions is summarized in **Table 1**.

Table 1. Schedule of Evaluations

Study Assessment	Baseline (Day 0)	Wk 1	Wk 2	Wk 4	Wk 4-8	Wk 12	Wk 24	Wk 36	Wk 48
Assessments									
Eligibility checklist	X								
Informed Consent/HIPAA	X								
Randomization	X								
Release of information ⁴	X			X			X		X
Limited history ⁵	X								
Concomitant medications	X								
Baseline Risk Assessments	X								
Follow-up Risk Assessments				X			X		X
Linkage to Care Assessment	X			X		X ⁶	X	X ⁶	X
STI Treatment/Referral Tracking ⁷	X								
Targeted physical examination	X								
Historical ART assessment	X								
ART Adherence Monitoring		X	X	X			X		X
Adverse Event Monitoring	X	X	X	X			X		X
Ensure Provision of ART	X ⁸	X	X	X ⁸					
ART acceptability survey				X					
Behavioral Services									
60 Min Intervention vs. Control	X								
Case Management	X	X ⁶	X ⁶	X					
Telephone follow-up		X	X						

Focus Group (optional)					X				
Laboratories									
INSTI HIV Rapid Test ⁹	X								
HIV Ultra RNA PCR	X						X		X
CD4/CD8 Panel	X								
GC/CT NAT (x3 sites)	X								
Syphilis EIA	X								
w/reflex to titer and TP-PA	X								
Comprehensive Metabolic Panel	X								
CBC w/diff	X								
HepBsAg	X								
HIV Genosure archive resistance test (w/Integrase)	X ³								

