Urine Pregnancy test ¹	X								
Specimen Collection									
Plasma Bank	X								
PBMC for cell pellet	X								
Stipends									
Study stipend ²	X			X	X		X		X

¹ In women any time pregnancy is suspected

² Compensation rates: Day 0 [\$20]; Survey Wk 4 [\$20]; Focus Group [\$50]; Wk 24 [\$50]; Wk 48 [\$75].

³ Sample is banked for future analysis

⁴ Baseline and at any time a new care provider is identified

⁵ Medical history, STI, HIV and Hepatitis

⁶ Phone call, email, text message, WhatsApp message, Facebook Messenger, and other participant-approved methods will be used to contact participant

⁷ Complete for participants who test positive for Syphilis, Gonorrhea and/or Chlamydia at their Day 0 visit

⁸ Study-provided ART will be dispensed at week 0 and 4

⁹ For participants without documentation of HIV positive test results

Antiretroviral Therapy (ART) drugs: Drugs proposed for use in the study are currently standard of care for PWH and are all FDA approved. For participants without a clinical history or documented evidence of integrase inhibitor resistance, a regimen of bictegravir, emtricitabine & tenofovir alafenamide (B/F/TAF) will be offered. For individuals with evidence of integrase inhibitor resistance, an alternative ART regimen will be determined, based on prior treatment regimens – in collaboration with the participants primary care physician.

Clinical assessments: All subjects will undergo history and physical examination at baseline (Day 0) for the purposes of documenting features consistent with HIV infection, subject demographics, income, insurance status and employment status. Adverse event monitoring and reporting will start at baseline and continue at each study visit. Serious adverse events, grade 2 rashes, and all grade 3 or 4 adverse events will be reported in line with the International Conference on Harmonization (ICH) guidelines.

Laboratory Assessments

HIV Monitoring Laboratories – All subjects will have an HIV rapid test performed on Day 0 on confirm HIV status if documentation of HIV status is not available to determine study eligibility. HIV related laboratories including: viral load (6 ml) and CD4 cell counts (3 ml). A 6 ml blood sample will be banked for future HIV drug resistance testing to assess ART resistance mutations (HIV GenoSure Archive). HIV viral load testing will be repeated at weeks 24 and 48.

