Pregnant individuals will be assisted in establishing care with HIV providers with experience in treating HIV in pregnancy and will assist with establishment in care with obstetrics providers with HIV expertise if not done prior to enrolment. The schedule of evaluations will remain the same for pregnant participants.

Data collection: data collection will be performed at each visit according to the schedule of evaluations and entered into the Research Electronic Data Capture (REDCap) data management system. Participants will be requested to provide release of information (ROI) to allow capture of HIV primary care visit data, primary care visit details (clinical notes) and HIV viral load for the duration of the study (48 weeks).

Primary outcomes are:

- the proportion of individuals with HIV VL ≤ 50 copies/ml at week 24; and
- the number of clinical care visits ≥ 90 days apart between study enrollment and week 24 (window +12 weeks).

Secondary outcomes are:

- the self-reported initiation of ART;
- the proportion of participants with HIV VL ≤ 50 at week 48;
- the proportion of participants with ≥ 2 clinical care visits > 90 days apart between enrollment and week 48;
- to compare discrete genotypic susceptibility score (derived from banked archive genotype at enrolment) between individuals with and without virologic suppression at week 24 and 48; and
- to assess the acceptability of rapid ART through quantitative surveys at week 4 and among four focus groups help between week 4-8.

Statistical considerations: Based on preliminary data from the 60-Minutes-for-Health pilot study, we expect a difference of 30% in the proportion of participants with suppressed viral load at week 24 between study groups. Assuming a loss to follow-up of 20% and a 70% rate of viral suppression in the intervention arm, we will need to enroll 124 individuals to detect a significant difference ($p < 0.05$) in suppression ($\geq 30\%$) between the two groups. The proportion of participants with the primary and secondary outcomes will be compared using Fisher's exact test between intervention groups. 95% confidence intervals for the overall proportion of PWH-OOC that are on ART with HIV VL ≤ 50 copies/ml and the overall proportion that are in care at week 24 will be compared to the analogous proportions among acute and early HIV (AEH) participants undergoing rapid ART initiation. Comparison with this historical cohort will be performed using Fisher's exact test.

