10. HUMAN SUBJECTS

We will enroll 124 participants in this study. Prospective participants will be identified through a number of means to ensure an equitable representation of PWH-OOC:

1. Potential subjects from UCSD Owen Clinic that fulfill the entry criteria will be contacted and offered an appointment for study recruitment
2. Subjects identified in the UCSD emergency department HIV screening program will be contacted and offered an appointment for study recruitment
3. San Diego Public Health Department (SDPHD) has implemented routine evaluations of their local HIV surveillance data in conjunction with other data to identify PWH who may be OOC³³. This Data to Care program results in the evaluation of ~ 250 new cases per year in San Diego (~20-21 PWH-OOC a month), many of whom are found to be viremic and out-of-care. Once located, SDPHD will offer immediate transportation vouchers (Lyft) to and from the AVRC to expedite study enrollment and rapid ART start.
4. If after 12 weeks enrollment falls below ~7/month we will initiate an additional social media campaign (Facebook and Instagram). We will use the existing UCSD AVRC platform to promote study participation and work within our existing partnerships with local gay bars to increase our social media reach.

Inclusion Criteria:

- 18 years of age or older;
- documented HIV infection status (or rapid HIV will be repeated);
- out-of-care defined as not seen in HIV provider clinic for ≥ 6 months AND not receiving ART for ≥ 1 month (by self-report);
- available for follow-up according to schedule of evaluations.

Exclusion Criteria:

- Co-morbid condition(s) that in the opinion of the investigator could limit the participant's ability to comply with the visit schedule or safely initiate rapid ART (e.g. psychiatric comorbidities or suspected central nervous system opportunistic infection);
- Prior ART regimens that in the opinion of the investigator precludes selection of a treatment option likely to result in virologic suppression (e.g. documented treatment failure on INSTI based regimen and multiple prior NRTI, NNRTI and PI regimens or documented resistance mutations likely to result in treatment failure)
- Participants that are unable to speak sufficient English or Spanish to consent to the study will be excluded

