15. RISK MANAGEMENT PROCEDURES AND ADEQUACY OF RESOURCES

Procedures taken to minimize risks to subjects are listed below:

- Loss of confidentiality: see section 16.
- Initiation of an ineffective HIV treatment regimen: The risk of using ineffective regimens will be minimized through obtaining as clear a history of prior ART regimens from the participant as possible, including using drug identification charts as standard. The proposed primary regimen (B/F/TAF) has a high barrier to resistance and resistance to this regimen in San Diego country is thought to be rare. The proposed study

follow-up timetable would be expected to rapidly identify cases of resistance allowing for regimen alteration in a timely manner.

- Phlebotomy will be undertaken by experienced practitioners to minimize discomfort.

Quality Assurance Monitoring and Record Availability: The AVRC quality assurance team will perform an on-site review of individual participant records, including: consent forms, CRFs, and laboratory specimen records. Monitoring will ensure protection of study participants, compliance with the protocol, and accuracy and completeness of records. The quality assurance team will also inspect regulatory files to ensure requirements are being met. Quality assurance monitoring will occur when 10 participants are enrolled and then at 6-month intervals during the remainder of study conduct. Participants will be monitored clinically and will be given the 24-hour number to call for emergencies. Participant will be informed to call at any time for adverse experience during study participation. This will be recorded in the research notes.

All deviations from protocol or unanticipated problems involving risk (UPR) to subjects, as defined by the UCSD UPR fact sheet, will be reported to the UCSD IRB within 10 days. Problems or events that do not fulfill the definition of a UPR will be summarized in a table and submitted to the IRB in a timely manner.

At year 1 and year 2 of full recruitment, the study team (PI, Co-Is) will review the data acquired and progress of the study. Details of virological failure will be reviewed for inadvertent initiation of an ineffective HIV treatment regimens.

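### Aim 3 compares the resistance score between all suppressed and all unsuppressed participants, so non-use of ART is mixed with resistance; an on-ART comparison should be reported beside it

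*Combined protocol and SAP*

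**What the plan says.** Section 6, Aim 3, treats the GSS "as a predictor of achieving virologic suppression on rapid ART among PWH-OOC". The secondary outcome in Section 9 that implements it takes a discrete score from the archive genotype banked at entry and compares it "between individuals with and without virologic suppression at week 24 and 48". It does not restrict to people taking ART, adjust for ART use, say which regimen is scored, or say how a missing viral load is classed. The only test named for secondary outcomes is Fisher's exact test between randomized arms, which is a different contrast.

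On drug supply, Section 9 says: "A 60-day supply of B/F/TAF or alternative will be provided for participants of both study arms". A footnote to Table 1 adds: "Study-provided ART will be dispensed at week 0 and 4". Viral load is then measured at weeks 24 and 48.

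On resistance, Section 15 says that "resistance to this regimen in San Diego country is thought to be rare". Section 10 excludes people whose prior regimens leave no option likely to suppress, giving "documented resistance mutations likely to result in treatment failure" as an example.

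Data on ART use are already planned: adherence monitoring at weeks 1, 2, 4, 24 and 48 (Table 1), survey items on regimen and adherence, and outside care records obtained under the release of information. The plan does not link any of these to the GSS outcome.

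**The concern.** A participant can be unsuppressed because the virus resists the regimen or because the regimen is not being taken. The score bears on the first cause only. Participants enter because they were out of care and off ART, resistance is expected to be rare, and known resistance is screened out or leads to another regimen. The unsuppressed group could therefore contain many people whose score had no chance to matter.

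The trial could then report that the archive genotype does not predict response to rapid ART, when it had largely compared people taking ART with people not taking it. Aim 3 is at stake; the primary comparison and the sample size are not.

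**Working it through.** **Inputs from Section 9, Statistical considerations.** "we expect a difference of 30% in the proportion of participants with suppressed viral load at week 24 between study groups". Also: "Assuming a loss to follow-up of 20% and a 70% rate of viral suppression in the intervention arm". The control rate is therefore 70% − 30% = 40%. Allocation is 1:1 and significance is p < 0.05. Power and sidedness are not stated; I assume 80% and two-sided.

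**1. The plan's own figure.** With a mean rate of 0.55:

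- n = [1.960 × √(2 × 0.55 × 0.45) + 0.842 × √(0.70 × 0.30 + 0.40 × 0.60)]² / 0.30² = 42.0 per arm.
- With continuity correction: (n/4) × [1 + √(1 + 4/(0.30n))]² = 48.4, so 49 per arm.
- With 20% loss: 49/0.80 = 61.25, so 62 per arm and 124 in total.

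This matches the stated 124 and supports reading the control rate as 40%.

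**2. Expected counts at week 24.** Evaluable: 124 × 0.80 = 99.2, or 49.6 per arm. Suppressed: 49.6 × (0.70 + 0.40) = 54.6. Unsuppressed: 49.6 × (0.30 + 0.60) = 44.6. Overall suppression S = 0.55.

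**3. Share of the unsuppressed who are not taking ART.** Let s be suppression among those taking ART (assumed; the documents give no value for this population), and treat everyone not taking ART as unsuppressed. The fraction taking ART is f = S/s, the off-ART share of the unsuppressed is (1 − f)/(1 − S), and on-ART failures number 99.2 × (f − S).

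| s (assumed) | f | Off-ART share of unsuppressed | On-ART failures |
|---|---|---|---|
| 98% | 0.561 | 97.5% | 1.1 |
| 90% | 0.611 | 86% | 6.1 |
| 80% | 0.688 | 69% | 13.6 |
| 70% | 0.786 | 48% | 23.4 |

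The share passes one half when f < 1 − 0.45/2 = 0.775, that is when s > 0.55/0.775 = 71%.

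If the 20% lost are instead counted as unsuppressed, S = 0.55 × 0.80 = 0.44. The share off ART or without a viral load becomes 98%, 91%, 80% and 66% for the same four values of s, and the threshold falls to 0.44/0.72 = 61%.

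**4. Effect on the GSS association (illustration).** Assume a low score in a fraction q of participants (10% to 30%), three times the on-ART failure risk with a low score, and stopping ART unrelated to the score. For s = 90% and q = 20%:

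- On-ART failure risk without a low score: 0.10/(3 × 0.20 + 0.80) = 0.0714; with one, 0.214.
- Low score among on-ART failures: 0.20 × 0.214/0.10 = 0.429.
- Low score among the suppressed: 0.20 × (1 − 0.214)/0.90 = 0.175.
- Low score among all unsuppressed: 0.864 × 0.20 + 0.136 × 0.429 = 0.231.
- Odds ratio on ART: (0.429/0.571)/(0.175/0.825) = 3.5. Among all participants: (0.231/0.769)/(0.175/0.825) = 1.4.

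Across q = 10% to 30%, with exact Fisher power for about 45 unsuppressed and 55 suppressed:

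| s | Odds ratio, on ART | Odds ratio, all | Power, on ART | Power, all |
|---|---|---|---|---|
| 98% | 3.1 | 1.1 | under 1% | 3–4% |
| 90% | 3.5–3.7 | 1.4–1.5 | 19–27% | 7–9% |
| 80% | 4.2–5.0 | 2.0–2.6 | 45–58% | 23–31% |

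**5. A cross-check that needs no value of s.** Counselling cannot change archived resistance, and randomization balances it on average. The planned 30-point difference must therefore act through engagement or adherence. That is 30 of the control arm's 60 points of non-suppression, or 0.30/(0.30 + 0.60) = one third of all the unsuppressed.

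**The case against.** Several counter-arguments have force.

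- **No proportion off ART is stated.** A reader might infer that most of the unsuppressed will be off ART because study drug covers only 60 days. The documents do not support that inference by itself: case management is meant to secure insurance and linked care, through which ART can continue. The 98% suppression in Section 7 comes from acute and early infection, not from people out of care. Poor adherence while still on ART is a further cause that step 3 does not separate. This stands, so the shares are conditional.
- **Drop-out is the wrong word.** A person lost without a viral load enters the comparison only if missing counts as failure, which the plan does not say. This stands.
- **The direction is not certain.** Dilution needs stopping ART to be unrelated to the score. Earlier treatment interruptions could drive both archived resistance and renewed disengagement. This stands.
- **Aim 3 may mean everyone who started under the rapid-ART strategy.** That is a legitimate question and a reason to keep the all-participant comparison. It does not make that comparison informative about resistance.
- **The restricted comparison has few failures and selects after baseline.** True. In the illustration it has more power than the all-participant comparison at 80% and 90% on-ART suppression, but almost none at 98%. Narrow variation in the score, from excluding known resistance, also limits both comparisons.
- **Rescoring on the week-24 regimen could hide early failures.** Section 15 anticipates regimen changes when resistance is found. This stands and shapes the fix.

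**Conclusion.** The concern holds in a conditional form. The outcome as written does not separate non-use of ART from resistance, although Aim 3 is worded around suppression on ART and the data to separate them are planned. People not taking ART are most of the week-24 unsuppressed group if on-ART suppression exceeds about 71% (about 61% if missing counts as failure). This rests on the planned 70% and 40%, on off-ART participants being unsuppressed, and on an on-ART rate that the documents do not give. No week-48 rate is planned, so the size at week 48 cannot be worked out.

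If stopping is unrelated to the score, the attenuation can be large: in the illustration an odds ratio of about 3.5 falls to about 1.4. Two stronger conclusions are not supported: that the comparison is known to reflect mainly drop-out, and that the bias is certain to run towards no difference. The matter affects a secondary aim of a study that describes itself as a feasibility study. It should be corrected but does not threaten the primary result.

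**What to change.** - For Aim 3, add a GSS comparison among participants with evidence of ART use at the week-24 and week-48 visits. Define that evidence in advance from the scheduled adherence monitoring, the regimen survey items and the released care records. Report it beside the all-participant comparison.
- Score the GSS against the regimen started at enrolment, with the regimen taken at the visit as a sensitivity analysis.
- Name the test for suppressed versus unsuppressed participants and the rule for missing viral loads, since the plan gives neither.
- State that a null all-participant result will not be interpreted as showing that resistance has no effect, and that excluding known resistance narrows the range of scores.

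The cost is some wording and a small amount of analysis, with no new visits or assays. The resistance sample is banked for later testing, so the rules can be fixed before any score is known. The drawbacks are that on-ART failures may number only about 1 to 14 (on-ART suppression of 98% down to 80%), which makes the result descriptive, and that ART use is partly self-reported and measured after baseline.

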4. ESTIMATED DURATION OF THE STUDY

3 years

5. LAY LANGUAGE SUMMARY OR SYNOPSIS (no more than one paragraph)

The human immunodeficiency virus (HIV) continues to cause significant illness and death in the USA despite availability of effective treatment. People who are aware of their HIV status, but who are out of care and not on medications, are therefore at risk of developing HIV related health problems. In addition, people with HIV who are out of care are at greater risk of transmitting HIV compared to people on HIV treatment with suppressed levels of virus in plasma. To date, there are no interventions that have been shown to successfully link this “out of care” population back into care and successfully maintain viral suppression.

This study will test a strategy of providing immediate HIV therapy drugs, linkage to care, and a randomized intervention (60-minutes for health or diet and nutrition session). The goal of the study is to demonstrate that the 60-Minutes-for-Health intervention improves the rate of viral suppression at 24 weeks.

The use of rapid antiretroviral therapy (rapid ART), defined as the initiation of ART within 7 days of HIV diagnosis, has been associated with improved rates of linkage to care, retention in care and virological suppression after 1 year among persons newly diagnoses with HIV. In addition, the behavioral intervention, “60-Minutes-for-Health”, was shown in a pilot study to improve retention in care among PWH-OOC. We aim to undertake a study to evaluate the feasibility of providing rapid-ART to people who are aware of their HIV status, but have been out of care at the time they re-engage in care. In addition, study participants will be randomized to either the “60-Minutes-for-Health” intervention or a 60 minute diet and nutrition control session.

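### Week 24 suppression is compared between arms by an unadjusted Fisher's exact test alone: no between-arm difference with a 95% CI is planned, and the scheduled Day 0 viral load is not used

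*Combined protocol and SAP*

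**What the plan says.** All references are to the combined protocol and SAP.

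- **Goal.** The lay summary (Section 5) states: "The goal of the study is to demonstrate that the 60-Minutes-for-Health intervention improves the rate of viral suppression at 24 weeks". Aim 1 in Section 6 is the same comparison between randomised arms.
- **Between-arm analysis.** Section 9, Statistical considerations: "The proportion of participants with the primary and secondary outcomes will be compared using" Fisher's exact test between the intervention groups. No risk difference, ratio, interval or covariate is named.
- **Intervals.** The next sentence plans "95% confidence intervals for the overall proportion of PWH-OOC that are on ART" and are suppressed, and for the overall proportion in care. Both are set against a historical cohort with acute and early HIV. They pool the two arms.
- **Design assumptions.** The effect size is given as follows: "we expect a difference of 30% in the proportion of participants with suppressed viral load at week 24 between study groups". The other two inputs to the sample size come in the sentence after it: "Assuming a loss to follow-up of 20% and a 70% rate of viral suppression in the intervention arm". The total is 124 at p < 0.05. Power and sidedness are not stated.
- **Baseline viral load.** Table 1 marks "HIV Ultra RNA PCR" at baseline, week 24 and week 48. Laboratory Assessments lists "HIV related laboratories including: viral load (6 ml) and CD4 cell counts (3 ml") and adds "HIV viral load testing will be repeated at weeks 24 and 48". The Day 0 value is not used as a covariate, a stratification factor or an entry criterion.

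The multivariate regressions mentioned under collaborations in Section 9 concern outside projects, not this comparison.

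**The concern.** The historical, non-randomised comparison gets confidence intervals, while the randomised comparison that is the study's goal gets only a p-value. Section 9 describes a feasibility study, whose readers need the size of the effect and how well it is known. At the planned effect the interval is wide, roughly 10 to 47 points, and a p-value does not show that.

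Two things follow. A non-significant Fisher result could be read as no difference when the planned 30 points are still compatible with the data. And if an interval is added after the data are seen, it can disagree with Fisher, which leaves room to choose between them.

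Separately, Day 0 viral load is the baseline measurement of the outcome variable. The inclusion criteria in Section 10 set no minimum viral load, and being off ART is by self-report, so some participants may enter with low values. If the Day 0 value predicts week 24 suppression, leaving it out gives away precision already paid for.

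**Working it through.** **1. The plan's own sample size.** Inputs from Section 9: p1 = 0.70, p2 = 0.70 - 0.30 = 0.40, loss 20%. Assumed: two-sided 0.05 and 80% power.

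- Uncorrected: n0 = [1.96·√(2·0.55·0.45) + 0.8416·√(0.70·0.30 + 0.40·0.60)]² / 0.30² = 41.97 per arm.
- Continuity-corrected: (n0/4)·[1 + √(1 + 4/(n0·0.30))]² = 48.41, so 49 per arm.
- Loss: 49/0.80 = 61.25, so 62 per arm and 124 in total.

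The stated 124 is reproduced, and the continuity-corrected formula suits Fisher's test.

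**2. Fisher against an unadjusted interval, 98 evaluable.** Power is the sum over all tables (x, y) of Bin(x; n1, 0.70)·Bin(y; n2, 0.40) for those that reject. Size is the same sum with equal rates. "z/CI" is the pooled z test or the Newcombe 95% CI excluding zero; their powers agree closely.

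| Evaluable, intervention v control | Fisher power | z/CI power | Gain (points) |
|---|---|---|---|
| 49 v 49 | 81.5% | 86.6% | 5.0 |
| 48 v 50 | 85.1% | 86.2% | 1.2 |
| 47 v 51 | 84.8% | 86.0% | 1.2 |
| 50 v 48 | 82.5% | 87.0% | 4.5 |
| Averaged over chance splits of 98 from 62 + 62 | 83.4% | 86.4% | 3.0 |

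Exact equality arises in only about 17% of such splits. Fisher's size is 2.9-3.3% at 49 v 49 (null rates 0.30 to 0.70) and about 4% at 48 v 50 or on average. At 49 v 49 the size of the z test or CI is 4.8-5.4%. The gain over Fisher therefore comes from using the full 5% level.

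The Newcombe CI excludes zero while Fisher's p is 0.05 or more in about 3% of trials on average at the planned effect, and in 5.0% at exactly 49 v 49. The reverse does not occur.

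**3. Two illustrative results at 49 per arm.** Newcombe limits combine the Wilson limits (l, u) of each arm: lower = d - √[(p1 - l1)² + (u2 - p2)²], upper = d + √[(u1 - p1)² + (p2 - l2)²].

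- 34/49 v 24/49: d = 20.4 points, CI +1.0 to +37.8, Fisher p = 0.064.
- 34/49 v 27/49: d = 14.3 points, CI -4.8 to +32.0, Fisher p = 0.21. The planned 30 points lie inside the interval.

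The first example is an equal-arm case, where disagreement is most likely. At exactly 70% v 40% the Newcombe CI is 10.3 to 46.6 points. The Wald half-width is 1.96·√(0.45/49) = 18.8 points.

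**4. Adjusting for log10 Day 0 viral load.** Simulation, 20,000 trials per setting, 49 per arm: logistic regression on arm and viral load, standardised risk difference, influence-function SE with n - 3 degrees of freedom and a t quantile. The ORs per SD are assumed. Ranges run from complete data with no values at the assay limit to 40% at the limit with 5% missing.

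| OR per SD (assumed) | Power | CI half-width (points) |
|---|---|---|
| 1 (not prognostic) | 85.7-86.4% | 19.1 |
| 1.65 | 87.0-87.5% | 18.6-18.7 |
| 2 | 88.0-88.7% | 18.2-18.4 |
| 2.72 | 90.4-91.3% | 17.5-17.8 |

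Against the z test's 86.6%, adjustment adds from 85.7 - 86.6 = -0.9 to 91.3 - 86.6 = +4.7 points. Null rejection is 4.7-5.5% over 27 settings, or 5.4-6.1% without the small-sample correction. Coverage is 94.6-95.2%.

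**5. If lost participants count as failures (assumed).** The rates become 0.8·70% = 56% and 0.8·40% = 32%, with 62 per arm. Fisher's power is 73.7%, the z test's 79.4%, and the adjusted analysis 78.1-81.8%.

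**The case against.** One could fairly reply that Fisher's test is valid, the sample size fits it, and naming a test does not forbid reporting the two proportions and their difference. The missing interval is cured by one sentence. The equal-arm figures flatter the change: move one evaluable participant from intervention to control and the gain falls from 5.0 to 1.2 points. The covariate's value is unknown, and the determinants that Section 9 does name (unmet need, substance use, mental health, stigma) do not include viral load. There are two primary outcomes and no multiplicity rule, so using the full 5% level on one of them has a price. And the rule for missing week 24 outcomes moves Fisher's power by 81.5 - 73.7 = 7.8 points, more than adjustment offers.

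Much of this stands. The power gain should be quoted as about 3 points, with the 5-point figure tied to exact balance. The covariate gain is an assumption and can be slightly negative. Fisher need not be dropped. Multiplicity is a real downside, and the missing-outcome rule must be settled separately.

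Two points remain. Silence does not commit anyone to an estimate, and since the interval and Fisher can disagree, their order has to be fixed beforehand. And the determinants listed are for engagement in care; Day 0 viral load is the baseline of the outcome itself and costs nothing more to collect.

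A reader might also infer that the trial is underpowered or the test wrong. The documents do not support that: 124 reproduces, and Fisher exceeds 80% power at 70% v 40% with 98 evaluable.

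**Conclusion.** The point holds as forgone precision and interpretability, not as an invalid or underpowered design. The missing between-arm estimate and interval is the stronger part and needs no assumption about prognosis. The unused baseline value is the weaker part.

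- **Unadjusted CI or z test over Fisher:** about 3 points of power on average, range about 1 to 5, obtained by using the full 5% level where Fisher uses about 3% to 4%.
- **Disagreement at the planned effect:** about 3% of trials, and 5% only with exactly equal arms.
- **Adjustment over the z test:** about -1 to +5 points for ORs of 1 to 2.72 per SD.

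These figures assume a two-sided 5% level, 98 evaluable participants and true rates of 70% and 40%. The ORs and the fractions undetectable or missing at Day 0 are assumptions. It would be tempting to conclude that Fisher costs 5 points in general or must be demoted to a sensitivity analysis. Neither follows: the first depends on exact balance, and one named primary estimate with its CI is enough.

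**What to change.** Before any comparison by arm, add to Statistical considerations:

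1. **Primary estimate.** The risk difference in week 24 suppression with a 95% CI, standardised from a logistic regression on arm and log10 Day 0 viral load. Use a small-sample SE (n - 3 degrees of freedom, t quantile). Set Day 0 values below the assay limit to that limit, and missing Day 0 values to the mean log10 value pooled over both arms.
2. **Reported beside it.** Both arm proportions, the crude risk difference with a Newcombe 95% CI, and the Fisher p-value.
3. **Decision rule.** One sentence stating which result is decisive, because the CI and Fisher can disagree.

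The cost is wording and slightly more analysis work, with no new visits, samples or participants. If the adjusted CI is decisive, Fisher's guaranteed level is exchanged for about 5% (4.7-5.5% in simulation), and the plan has two primary outcomes without a multiplicity rule. If viral load is not prognostic there is no covariate gain, and up to about 1 point of power is lost against the z test. The rule for missing week 24 outcomes must be set separately, since it defines who enters the regression.
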